5.8.1 Interaction with other drugs

Interaction of giredestrant (GDC-9545) with other medicinal products and other forms of interaction

Giredestrant is a moderately sensitive CYP3A substrate. Co-administration giredestrant with the strong CYP3A inhibitors and inducers should be avoided. Refer to the giredestrant's (GDC-9545) IB for a complete summary of safety information and DDIs.

Interaction of tamoxifen with other medicinal products and other forms of interaction

When tamoxifen is used in combination with coumarin-type anticoagulants, a significant increase in anticoagulant effect may occur. Where such co-administration is initiated, careful monitoring of the patient is recommended.

As tamoxifen is metabolized by cytochrome P450 3A4, care is required when co-administering with drugs, such as rifampicin, known to induce this enzyme as tamoxifen levels may be reduced. The clinical relevance of this reduction is unknown. Therefore, is recommended to avoid the coadministration of tamoxifen and CYP3A inhibitors/inducers.

Pharmacokinetic interaction with CYP2D6 inhibitors, showing a 65-75% reduction in plasma levels of one of the more active forms of the drug, i.e., endoxifen, has been reported in the literature. Reduced efficacy of tamoxifen has been reported with concomitant usage of some SSRI antidepressants (e.g. paroxetine) in some studies.

As a reduced effect of tamoxifen cannot be excluded, co-administration with potent CYP2D6 inhibitors (e.g. paroxetine, fluoxetine, quinidine, cinacalcet or bupropion) should whenever possible be avoided.

6 ASSESSMENTS AND STUDY PROCEDURES

6.1 Patient entry procedures

6.1.1 Informed consent

Written informed consent from the patient (or the patient's legally authorized representative) must be signed and dated before her participation in the study and before performing any study specific procedure. Patients will be informed as to the nature of the study drug and will receive pertinent written information regarding the study objectives, possible benefits, and potential AEs. They will also receive information on the follow-up procedures and possible risks they will be exposed to. The informed consent form will also inform patients about how biological samples will be obtained and collected and its legal implications. A copy of the signed ICF must be provided to the patient or the patient's legally authorized representative. Patients have the right to voluntarily withdraw from the study at any time for any reason, and this will not affect any future medical treatment the patient will receive.

6.1.2 Patient allocation

The following steps must be taken before registering patients to this study:

1. Completion of patient eligibility checklist by the investigational site, once checked all selection criteria. For patients with locally determined basal Ki67 between 10% and 19%, after receiving central Ki67 score result.

Note for Ki67 selection criteria: Ki67 will be analyzed locally at the time of inclusion. For patients with basal Ki67 $\geq 20\%$ according to local analysis, Ki67 $\geq 10\%$ will be centrally confirmed retrospectively after inclusion. For patients with basal Ki67 levels between 10% and 19% according to local analysis, Ki67 $\geq 10\%$ will need to be centrally confirmed before inclusion.

2. Registration of patient in the Sponsor's study database.
3. Randomization using Sponsor's study database.

Confirmation of patient allocation using Sponsor study database:

Each patient will be identified with a unique patient number (UPN) for this study obtained from eCRF. All data will be recorded with this identification number on the appropriate eCRFs.

Confirmation of patient's eligibility for study participation will be recorded on the eCRF by the investigational site and verified by the study medical monitor prior to inclusion (all screening data needs to be completed 48h prior to randomization to allow enough time for medical monitor review). The investigator is responsible for safeguarding patient information (i.e., age, name, address, telephone number, social security number, and study identification number), ensuring access to this information by Health Authorities if necessary. These records will remain confidential for the period of time stipulated by current legislation.

Randomization

Premenopausal women with ER[+]/HER2[-] and Ki6 $\geq 10\%$ early breast cancer will be randomized in a 1:1 ratio to giredestrant (GDC-9545) or tamoxifen arms.

Randomization will be accomplished using an automated web randomization system (eCRF provided by the Sponsor). The system contains the randomization schedule. At the screening visit, the investigative site will obtain the patient number from the eCRF and will contact randomization system (online). The site will enroll the patient by indicating minimal information sufficient to distinguish one patient from another and receive the patient identity (ID) number. At the baseline visit, the system will associate that patient with the next available treatment on the randomization schedule and provide the randomization number.

Refer to the separate study manual for instructions for study entry, patient ID assignments, and randomization procedures.

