The phase II coopERA trial (NCT04436744) was a two arm, open-label, multicenter trial aimed at evaluating the efficacy, safety and pharmacokinetics of giredestrant (GDC-9545) plus palbociclib compared with anastrozole plus palbociclib in postmenopausal women with untreated ER-positive/HER2-negative EBC. 221 patients with baseline Ki67 score $\geq 5\%$ were randomized 1:1 to receive 14 days of anastrozole (1 mg, PO QD) or giredestrant (GDC-9545) (30 mg, PO QD) (window-of-opportunity phase, WoO) followed by 16 weeks (four 28-days cycles) of additional neoadjuvant palbociclib (125 mg, PO, D1-21) treatment prior to surgery. The primary objective of the study was to measure tumoral Ki67 changed between baseline and post-WoO samples. In ESMO Breast 2021, preliminary results were shown for 83/202 planned patients. Two-week relative Ki67 reduction was significantly greater with giredestrant (GDC-9545) than anastrozole (80% versus 67%, respectively) and a consistent Ki67 suppression was observed in patients with baseline Ki67 $\geq 20\%$ (giredestrant (GDC-9545): 83% reduction; anastrozole: 71%) or $< 20\%$ (65% vs 24%). After 14 days of treatment, 25% of tumors exhibited complete cell cycle arrest (secondary objective) with giredestrant (GDC-9545) versus 5% with anastrozole. Patients treated with giredestrant (GDC-9545) had fewer AEs than anastrozole.

Table 2 summarizes ongoing clinical trials with giredestrant (GDC-9545) for the treatment of early or advanced hormonal receptor-positive BC. In addition, giredestrant (GDC-9545) is also being studied in the treatment of ER-positive/HER2-positive BC.

Table 2. Ongoing clinical trials with giredestrant (GDC-9545) in BC.

Clinical Trial	Phase	Study
NCT03916744	I	A Phase I, Multicenter, Open-Label Preoperative, Short-Term Window Study of GDC-9545 in Postmenopausal Women With Stage I-III Operable, Estrogen Receptor-Positive Breast Cancer
NCT03332797	Ib/II	Multicenter, Open-Label, Dose Escalation, Dose Expansion Study Evaluating the Safety, Pharmacokinetics, and Activity of GDC-9545 Alone or in Combination With Palbociclib and/or LHRH Agonist in Patients With Locally Advanced or Metastatic Estrogen Receptor-Positive Breast Cancer
NCT04802759	Ib/II	Open-Label, Multicenter, Randomized Umbrella Study Evaluating the Efficacy and Safety of Multiple Treatment Combinations in Patients With Breast Cancer (MORPHEUS-Breast Cancer)

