8.2 Sample size

The analysis will compare absolute changes for Ki67 expression between baseline score and the evaluation after the treatment. The sample size was based on a superiority contrast between two study arms analyzed with a two-sided t-test set at 0.05 alpha level. We assumed a 70% mean in giredestrant (GDC-9545) Arm vs. 50% mean in tamoxifen with a 29% common standard deviation, according to the results observed (Dowsett, Smith, et al., 2005). We planned 34 patients per arm to attain an 80% power.

The final analysis will be conducted with unpaired Wilcoxon test because of the non-asymptotic distribution of data. We assumed that asymptotic efficiency of Wilcoxon test relative to the t-test, never falls below 0.86 (Jr & Lehmann, 1956). In addition, we expect a 10% dropout rate. So, 46 patients per arm will be finally recruited. We used the R software version 4.0.2. released on 2020-06-22 ("pwr").

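### The primary Wilcoxon test ignores baseline Ki67; stratifying it by the local Ki67 band already known at randomisation would protect it against chance imbalance and add power at no extra patients

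*Protocol*

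**What the plan says.** **Allocation.** Protocol 6.1.2 gives a 1:1 ratio through a web system. At screening the site enrols the patient by "indicating minimal information sufficient to distinguish one patient from another"; at the baseline visit "the system will associate that patient with the next available treatment on the randomization schedule". No stratum, block size or minimisation factor appears in the Protocol or the SAP. Procedural detail is referred to a separate study manual.

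**The band.** The same section makes the local Ki67 result decide the route into the trial. "For patients with basal Ki67 levels between 10% and 19% according to local analysis", central confirmation must come before inclusion; at a local value of 20% or more it comes afterwards. Every site therefore knows the band before it randomises.

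**Primary test.** Protocol 8.4 and SAP 4.4.1 test the absolute difference in central Ki67 with a two-sided unpaired Wilcoxon test at 0.05 in the mITT set, with treatment as the only factor. Superiority is declared on that test. Regression on baseline Ki67 is planned, but only as a supportive analysis (Protocol Table 6 and SAP Table 1, IDs 4-6).

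**Sample size.** Protocol 8.2 and SAP 1.6 assume a "70% mean in giredestrant (GDC-9545) Arm vs. 50% mean in tamoxifen with a 29% common standard deviation", analysed with a "two-sided t-test set at 0.05 alpha level".

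**The concern.** The response is measured in absolute Ki67 points, so it scales with the starting value: a tumour at 12% cannot fall by more than 12 points. A rank test that ignores baseline partly ranks patients by where they started. If one arm draws more high-Ki67 tumours by chance, it looks better whatever the drug does. Even in a balanced trial, the spread in baseline adds noise that hides a real difference.

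With about 41 evaluable patients per arm such imbalances are not rare. The decisive analysis has no protection against them, although the information needed is already in hand for every patient.

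**Working it through.** **1. The plan's own figure.** Difference 20, SD 29, two-sided alpha 0.05, power 80%: the t-test solution is 33.99 per arm, so 34. This matches "We planned 34 patients per arm to attain an 80% power". Allowing for "asymptotic efficiency of Wilcoxon test relative to the t-test, never falls below 0.86": 34/0.86 = 39.5, so 40. With 10% dropout: 40/0.90 = 44.4, so 45, against the stated 46 (40 x 1.15 = 46). The figure is reproduced to within one patient. Evaluable per arm: 46 x 0.90 = 41.4, so 41 is used below.

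**2. Why baseline matters.** Apply the plan's mean falls to two illustrative baselines:
- Baseline 15%: giredestrant 0.70 x 15 = 10.5 points; tamoxifen 0.50 x 15 = 7.5.
- Baseline 30%: giredestrant 0.70 x 30 = 21 points; tamoxifen 0.50 x 30 = 15.

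The tamoxifen patient at 30% (15 points) outranks the giredestrant patient at 15% (10.5 points).

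**3. How often the bands are unbalanced.** The SD of the difference in band share is sqrt(2p(1-p)/n). With n = 41 and an assumed 60% at >=20%: sqrt(2 x 0.6 x 0.4/41) = 0.108. A gap of 15 points or more means at least 7 of 41 patients. With continuity correction, (6.5/41)/0.108 = 1.47, a two-sided probability of about 14%. With 70%: SD 0.101, ratio 1.57, about 12%. For all 46 randomised per arm and shares of 50-80%, exact binomial calculation gives 9-17% for 15 points or more and 1-5% for 20 points or more.

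**4. Effect on the tests (simulation, 41 per arm).** The relative fall is normal with SD 29 and mean 50/50 (null) or 70/50, times baseline. The documents give no baseline distribution, so three were assumed:
- A: lognormal, median 22%, log-SD 0.5, truncated at 10%, local-central disagreement log-SD 0.2.
- B: as A, with median 25% and log-SD 0.6.
- C: uniform 10-20% in the low band, 20% plus a gamma variable of mean 14 in the high band, with 50-70% in the high band.

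The van Elteren statistic sums, over the two bands, the rank sum minus its expectation, weighted by 1/(N_h + 1), where N_h is the number of patients in band h.

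Power under 70/50:

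| Baseline | Plain Wilcoxon, simple list | Van Elteren, simple list | Van Elteren, stratified list |
|---|---|---|---|
| A | 0.60 | 0.70 | 0.70 |
| B | 0.55 | 0.66 | 0.66 |
| C (70% high band) | 0.58 | 0.74 | 0.74 |

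No drug difference:
- Plain Wilcoxon over all trials: 0.049 (C, 60% high band) and 0.052 (A).
- Plain Wilcoxon in trials with a band gap of 15 points or more: about 8-13% across runs under A and B. Part of that spread is simulation error: 4,000 trials x 0.14 = 560 trials, and sqrt(0.10 x 0.90/560) = 1.3 points.
- Van Elteren in the same trials: about 4-6%.

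Direction (C, 60% high band, gap of at least 6 of 41 = 14.6 points, about 11% of trials each way):
- No drug effect, more high-band patients on giredestrant: 11.8% false positives favouring giredestrant, or 6.1% if 20% of local bands disagree with central.
- True 70/50, fewer high-band patients on giredestrant: power 0.17 (0.36 with that disagreement). With more high-band patients on giredestrant: 0.91 (0.79). Balanced: 0.59 (0.56).

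**5. Stratifying the list alone.** In C, plain Wilcoxon power moves only from 0.57 to 0.59. Its null rejection falls to 0.025, or 0.041 with 20% disagreement: conservative, with almost no gain.

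**The case against.** **Type I error is already controlled.** This stands. Averaged over all randomisations the planned test rejects at about 5%. The excess exists only conditionally on an unbalanced trial, and gaps of 20 points or more are uncommon.

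**The plan already adjusts for baseline.** In part. IDs 4-6 would expose an imbalance, but superiority is declared on the unadjusted test, and no rule says what follows if the two disagree.

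**The list may be stratified after all.** Possible. The Protocol defers to a study manual that was not available, and the phrase about minimal information describes enrolment at screening, not the allocation step. A reader might infer that the system holds no baseline data, or that a single unstratified list is established. The documents show only that no stratum is named. The point does not depend on this, because the planned test uses no stratum either way.

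**The external evidence on the band is weak.** Agreed. Protocol 1.5.1 reports relative falls of 83% against 65% (giredestrant) and 71% against 24% (anastrozole) for baseline >=20% against <20%. These are preliminary data on 83 of 202 planned patients, postmenopausal, with entry at Ki67 >=5%, so the lower group includes tumours this trial excludes. The argument rests on the absolute scale of the endpoint instead.

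**The local band is only a proxy for central Ki67.** True. Disagreement reduces both the risk and the benefit. The mITT set also drops patients after randomisation, so even a stratified list would not guarantee balance in the primary set.

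**Conclusion.** The point holds against the primary analysis. An unadjusted test of absolute change discards a strong predictor that is known before allocation. In the roughly 11-14% of trials with a band gap of 15 points or more, its false-positive rate is about 8-13% instead of 5%. The band-stratified test brings this back to about 4-6% and raises power from about 55-60% to about 66-70% (A and B; C gives a somewhat larger gain).

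Two stronger readings are tempting and not supported. One is that the randomisation list is the fault and that stratifying it is the remedy: van Elteren power is the same with either list, so the gain comes from the analysis. The other is that the trial's type I error is inflated: overall it is not.

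The sizes rest on assumed baseline distributions, an assumed 60-70% of patients at >=20%, and relative falls that do not depend on baseline; the direction held in every setting tried. That power stays below 80% even after the change reflects a separate matter: the 70%/50%/29% inputs behave as relative falls, while the test is on absolute points.

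**What to change.** 1. In Protocol 8.4 and SAP 4.4.1, make the primary test a two-sided Wilcoxon test stratified by local Ki67 band (10-19% or >=20%, van Elteren) at 0.05. Amend ID 1 in Protocol Table 6 and SAP Table 1. Keep the unstratified Wilcoxon as supportive, and say that the stratified test decides superiority.
2. Fix this before database lock. The trial is open-label and the Steering Committee reviews efficacy data (Protocol 8.11), so record that the change was made without sight of central Ki67 by arm. Enter it in SAP section 6, which now reports no changes from the Protocol.
3. Confirm that the local Ki67 value, and hence the band, is in the database for every randomised patient.
4. If enrolment is still open, the band may also be entered as a randomisation stratum, but only together with the stratified test. This may come too late: the Protocol is dated November 2023 with 16 months' accrual planned, and the SAP cites an eCRF accessed in February 2025.

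Cost: a protocol amendment and a short SAP change. No extra patients, samples or visits; N stays at 92. Step 4 adds one field before allocation.

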6.2 Visit schedule

After confirming eligibility through the screening process as indicated above, patients will be scheduled for baseline visit at day 1 (D1) of treatment within 48 h after randomization.

All screening tests and evaluations must be completed within the protocol scheduled time windows and reviewed to confirm that patients meet all eligibility criteria within 28 days prior to the first administration of study medication (dosing). The investigator will maintain a screening log to record details of all patients screened and to confirm eligibility or record reasons for screening failure, as applicable.

The study will consist of a screening period of up to 28-day, a window-of-opportunity 15-day treatment phase, an EoT visit (+ 1 day) and an EoS visit (28 days +/- 3 days after the final dose of study treatment). If post-treatment biopsy cannot be obtained within + 1 day from last day of treatment (15 days), treatment will be extended to 16 days and surgery or biopsy may be performed on the following day (be it D15 + 2 days).

Assessments scheduled for day 1 (before treatment) must be performed within 48 hours prior to study treatment administration, unless otherwise indicated in the schedule of assessments, to

confirm to the patient if treatment can be followed up. If a mandatory procedure described in the protocol falls on a bank holiday and/or weekend, this procedure should be performed on the day before or after the holiday (i.e. within a period of ± 2 working days), except for the time window for the End of Treatment visit tumor biopsy that should be collected at Day 15 (+ 1 day). If post-treatment biopsy cannot be performed within + 1 day from last day of treatment (that is, on D15 or D15+1), treatment will be extended to 16 days and surgery or biopsy will be performed the day after.

The summary of study assessments is included in **Appendix 1: Schedule of study assessments and procedures.**

6.3 Demographic data and medical history

Demographic data include age, sex, and self-reported race/ethnicity. Medical history comprises clinically significant diseases, surgical interventions, history of cancer (including prior antineoplastic treatments and procedures), history of smoking, alcoholism, drug addiction, as well as any medications (i.e., prescribed drugs, over-the-counter drugs, medicinal plants, homeopathic remedies, or food supplements) used by the patient in the 7 days prior to screening visit.

6.4 Tumor assessments

Assessment of primary tumor and regional lymph nodes must be performed by physical examination at screening and prior to administration of study treatment.

Patients must have histologically confirmed ER[+]/HER2[-] primary invasive adenocarcinoma of the breast with locally analyzed and centrally confirmed Ki67 $\geq 10\%$ and tumor size ≥ 1.0 cm in longest diameter by ultrasound.

6.4.1 Ki67 score assessment

A Ki67 score $\geq 10\%$ stained nuclei from the pre-treatment tumor tissue sample is required for eligibility. Ki67 score will be analyzed locally at the time of inclusion. For patients with basal Ki67 $\geq 20\%$ according to local analysis, Ki67 $\geq 10\%$ will be centrally confirmed retrospectively after inclusion. For patients with basal Ki67 levels between 10% and 19% according to local analysis, Ki67 $\geq 10\%$ will need to be centrally confirmed before randomization.

To assess eligibility, HER2, ER, PgR will be locally determined on the most recent tumor biopsy acquired at baseline prior to beginning of study treatment.

6.4.2 Tumor imaging assessment by ultrasound

Breast ultrasound and axillary node lymph status assessment should be performed according to institutional practice and result must be known at screening to assess eligibility and tumor size prior to randomization.

All known sites of disease must be documented at screening. Baseline staging to document absence of metastatic disease should be performed as per institutional practice, in alignment with

national guidelines, in patients where there may be a reasonable suspicion of advanced disease (e.g., clinically positive axillary lymph nodes, signs and symptoms). If done, it must be performed within 28 days prior to randomization and reports of these examinations must be available at site. Examination type for tumor staging is at the discretion of the investigator and can include i.e. X-ray, sonography, bone scan, CT, MRI, and/or PET-CT scan.

Patients diagnosed with multifocal or multicentric breast cancer will be eligible for the study if the two largest lesions meet pathologic criteria for ER positivity and HER2 negativity and at least one tumor lesion measures ≥ 1 cm in the longest diameter by ultrasound (reference lesion) and this one meets the histologic inclusion criteria of Ki67 score $\geq 10\%$ as described in Section 6.4.1.

6.5 Safety and tolerability assessments

6.5.1 Laboratory assessments

Laboratory tests will be performed in accordance with local standard treatment and clinical indications before treatment administration. These values should include: hematological test (hemoglobin, hematocrit, red blood cell count, platelet count, WBC and differential count [ANC, lymphocytes, monocytes, eosinophils and basophils, and other cells]); coagulation (INR, PTT (or aPTT)); chemistry panel (serum or plasma): sodium, potassium, chloride, glucose, BUN or urea, creatinine, total protein, albumin, phosphate, calcium, total bilirubin (if total bilirubin is $2 \times$ ULN, also direct bilirubin), AST, ALT, ALP, urate and LDH; fasting lipid panel: cholesterol, LDL cholesterol, HDL cholesterol, and triglycerides (after ≥ 8 hours of fasting); urinalysis, including dipstick (pH, specific gravity, glucose, protein, ketones, and blood) and microscopic examination (sediment, RBCs, WBCs, casts, crystals, epithelial cells, and bacteria), FSH and estradiol. Urinalysis should be performed as clinically indicated during study treatment.

6.5.2 Pregnancy and assessment of fertility

Premenopausal status is defined as estradiol (E2) in the premenopausal range (according to institution parameters) or patient has been menstruating regularly during the 6 months prior to randomization and has not used any form of hormonal contraception or any other hormonal treatments during this time.

All patients must undergo a serum pregnancy test at screening to confirm eligibility in the trial and within 14 days prior to initiation of study treatment (with result available prior to dosing), and a urine pregnancy test (with results available prior to dosing) within 24 hours prior to study treatment initiation.

All patients must remain abstinent and truly abstains from sexual activity (refrains from heterosexual intercourse) or use of locally recognized adequate methods of contraception (described as that with a failure rate $< 1\%$) during the length of the study, and to continue its use for 10 days after the last dose of study treatment (for patients taking giredestrant) or 60 days

following cessation of therapy (for patients in the tamoxifen arm). They must, as well, agree to refrain from donating eggs during the same period.

Examples of non-hormonal contraceptive method with a failure rate of <1% per year are bilateral tubal ligation, male sterilization and copper intrauterine devices.

The reliability of sexual abstinence should be evaluated in relation to the duration of the clinical trial and the preferred and usual lifestyle of the individual. Periodic abstinence (e.g., calendar, ovulation, symptothermal, or post ovulation methods) and withdrawal are not adequate methods of contraception.

An additional pregnancy test is indicated in the EoT visit and in the EoS visit, when a urine pregnancy test should be performed.

In case of pregnancy during study treatment or within 10 days after the last dose of study treatment (for patients taking giredestrant) or 60 days following cessation of therapy (for patients in the tamoxifen arm), the patient must permanently stop study treatment immediately and/or withdraw from the trial, and the pregnancy must be reported on the Clinical Trial Pregnancy Form as specified in **Section 7.2.4**.

